Our overall goal is to determine the change in bladder symptoms after preemptive pudendal nerve block before hydrodistention in patients with IC/PBS. In order to effectively characterize our outcomes we have chosen different validated instruments to assess post-operative pain. First, in order to objectively quantify pain intensity we will determine the mean difference in postoperative pain at 2 hours in the treatment group (1% Lidocaine) compared to the placebo group (saline) using the Visual Analog Scale (VAS); this will serve as our primary endpoint (AIM 1). In order to capture the most important voiding and pain symptoms and to assess the degree of bother between the two groups we will measure mean difference in interstitial cystitis symptom index and the problem index (O’Leary-Sant) and in the Pelvic pain, Urgency and Frequency (PUF) questionnaire at baseline, 2 hours, 2 weeks, 6 weeks and 3 months after treatment with hydrodistention and preemptive pudendal nerve block compared to hydrodistention with placebo (AIM 2). Finally in an attempt to expand our knowledge about the change in bladder symptoms over time, we will measure the change in the interstitial cystitis symptom index and the problem index (O’Leary-Sant) and in the Pelvic pain, Urgency and Frequency (PUF) questionnaire at baseline, 2 hours, 2 weeks, 6 weeks and 3 months

after treatment (AIM3). With this project we propose a novel approach to decreasing the immediate postoperative pain and possibly prolonging the efficacy of this intervention for the management of IC/PBS.

Aim 1. To determine the mean difference in pain at 2 hours postoperatively in patients undergoing hydrodistention with preemptive pudendal nerve block (1% Lidocaine) compared to hydrodistention with placebo (saline) using the visual analog scale (VAS).

AIM 2. To determine the mean difference in interstitial cystitis symptom index and the problem index (O'Leary-Sant) and in the Pelvic pain, Urgency and Frequency (PUF) questionnaire at baseline, 2 hours, 2 weeks, 6 weeks and 3 months after hydrodistention with preemptive pudendal nerve block (1% Lidocaine) compared to hydrodistention with placebo (saline).

AIM 3. To measure the change in the interstitial cystitis symptom index and the problem index (O'Leary-Sant) and in the Pelvic pain, Urgency and Frequency (PUF) questionnaire at baseline, 2 hours, 2 weeks, 6 weeks and 3 months after treatment with hydrodistention with and without preemptive pudendal nerve block.

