This study is a prospective double-blinded randomized controlled study that will be done at two sites: Johns Hopkins Bayview Medical Center and Greater Baltimore Medical Center. Female patients over 18 years of age, who present for treatment of painful bladder syndrome (IC/PBS) at the Pelvic Floor Center at the Johns Hopkins Bayview Medical Center, will be considered for inclusion in the study (please see below for inclusion and exclusion criteria). The primary investigator and co-investigators will determine patient eligibility. The patients will be asked to participate in the study if they are undergoing cystoscopy with hydrodistention for a presumed diagnosis of IC/PBS. When the patient presents to the operating room on the day of their scheduled surgery they will be asked to complete the PUF questionnaire, the interstitial cystitis symptom and problem index, and the Visual Analog Scale (VAS). This time point has been chosen to minimize the temporal variation seen in pain. Patients will be randomized to either preemptive bilateral pudendal nerve block with either 20 cubic centimeters 1% lidocaine or 20 cubic centimeters normal saline after anesthesia induction, participants will be stratified by type of anesthesia. The circulating nurse will be provided with a sealed opaque envelope with the patient group allocation and he/she will provide the operating surgeon with the study drug in a syringe labeled "pudendal nerve block". The placement of the pudendal nerve block will be performed in a standardized fashion per protocol. The patients will receive their standardized anesthetic regiment per anesthesiology guidelines. At the conclusion of the case the patients will be monitored in the postoperative anesthesia unit for recovery per nursing guidelines. The patients will be asked to rate their pain on a 100mm VAS, the O'Leary Sant, and the PUF at 2 hours postoperatively.

- b. Study duration and number of study visits required of research participants.

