The interstitial cystitis symptom index and the problem index and PUF questionnaire and VAS will be repeated at 2 hours, 2 weeks, 6 weeks and 3 months postoperatively via a telephone interview. These time points have been specifically chosen due to their common use as intervals for assessing pain. Additionally, the expected difference in pain intensity for these time intervals is well described in the literature¹⁷. Furthermore, the mean duration of action of cystoscopy with hydrodistention is reported to last between 2 and 6 weeks, and we will be certain to capture evidence of prolonged efficacy if study follow up is extended to 3 months post operatively^{17, 18, 19}.

- c. Blinding, including justification for blinding or not blinding the trial, if applicable.

Randomization to 1% Lidocaine versus placebo will be performed using computer or hand generated 1:1 block permutations and stratified by anesthesia type. Assignment will be revealed in the operating room after the patient receives anesthesia. We will randomize 120 patients total (60 at each site, 30 for placebo and 30 for treatment).

- d. Justification of why participants will not receive routine care or will have current therapy stopped.

Currently, hydrodistention is routinely done without pudendal nerve block. This study will introduce an addition to standard care that may alleviate postoperative pain.

- e. Justification for inclusion of a placebo or non-treatment group.

This study requires a placebo as this will allow for a comparison group, will enable us to account for a placebo effect and potential bias. However, both groups will be receiving standard treatment, which is hydrodistention.

- f. Definition of treatment failure or participant removal criteria.

Participants may be removed from the study if they are diagnosed/newly recognized to meet any of the exclusion criteria, including intolerance of local anesthesia, new bleeding disorder, or new onset mental status change that precludes the patient from being able to follow instructions or accurately assess pain control.

- g. Description of what happens to participants receiving therapy when study ends or if a participant's participation in the study ends prematurely.

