The PUF questionnaire is a commonly used measure for evaluating patients suspected of having IC/PBS. Its domains address what are considered the hallmarks of the disease, namely pain, urinary urgency, and frequency of urination³². Parsons et al. initially examined the value of the PUF questionnaire as a predictive diagnostic tool in 2002. In this study, a direct correlation was found between greater PUF scores and the likelihood of a positive PST in patients with suspected IC/PBS and gynecologic pain³³. Since then the PUF questionnaire has been considered a valid diagnostic screening tool for patients with possible IC/PBS and will be the tool used in this study for that purpose.

c. Statistical plan including sample size justification and interim data analysis.

Recent evidence suggests a significant difference in 2-hour postoperative mean VAS scores after preemptive analgesia with 1% lidocaine (50.1 ± 27.9) compared to placebo (70.6 ± 22.6)³⁴. Based on this estimated mean difference we are planning this study with 50 participants ($n = 50$). The Type I error probability associated with the test of this null hypothesis is 0.05, with a power of 80%. Demographic, surgical, and clinical outcomes will be assessed using t-test, chi squared, and Fisher exact tests where appropriate. For continuous measures, normally distributed data will be compared with Students t test; non-normally distributed data will be compared with Wilcoxon test. Visual analog pain scores will be compared using repeated measures of variance. Furthermore, an intention to treat analysis will be performed for the participants who drop out prior to study completion.

d. Early stopping rules.

- e. Participants who no longer wish to be a part of the study may stop without penalty at any time during the study.

8. Risks

- a. Medical risks, listing all procedures, their major and minor risks and expected frequency.

There is minimal risk involved in performing pudendal nerve blocks, these risk include a less than 1% chance of additional pain, bleeding, hematoma or lidocaine systemic toxicity.

- b. Steps taken to minimize the risks.

In order to minimize risk the pudendal nerve block will be performed by a trained urogynecologist in the operating room, additionally the patients will be monitored by an anesthesiologist during the procedure for any signs of systemic toxicity.

The participants will also be monitored in the postoperative recovery area for 2 hours after their procedure.

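### Randomization is stratified by anesthesia type, but the planned 2-hour VAS comparison names no term for it; if type predicts early pain, the interval is too wide and some power is lost.

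*Combined protocol and SAP*

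**What the plan says.** Aim 1 in section 2 defines the primary question: "To determine the mean difference in pain at 2 hours postoperatively in patients undergoing hydrodistention with preemptive pudendal nerve block", against saline, on the VAS.

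Anesthesia type appears twice as a design factor. Section 4a states that "participants will be stratified by type of anesthesia". The randomization text in section 4c specifies "block permutations and stratified by anesthesia type". On the anesthetic itself, section 4a says only this: "The patients will receive their standardized anesthetic regiment per anesthesiology guidelines". No types, expected shares or durations are listed, although stratifying presupposes at least two types.

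Section 7c offers the t test or the Wilcoxon test for continuous measures, and chi-squared or Fisher tests elsewhere. For the primary measure it says: "Visual analog pain scores will be compared using repeated measures of variance". It mentions no anesthesia-type covariate, stratified test, interaction or by-type summary, and no other section supplies one.

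**The concern.** Permuted blocks within anesthesia type balance the arms within each type. A pain difference between types therefore hardly enters the true sampling error of the arm difference. An analysis that leaves type out still counts that difference as residual noise, so the estimated standard error exceeds the true one.

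The sponsor's choice of this factor suggests that it was expected to matter for an early pain score. If it does, three things follow for Aim 1: the confidence interval is wider than the design justifies, the test is stricter than its stated 5%, and part of the planned power is lost. At the sample size justified in 7c there is little power to spare.

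**Working it through.** **Inputs from section 7c.** Means and SDs: "1% lidocaine (50.1 ± 27.9) compared to placebo (70.6 ± 22.6" mm. Error rate 0.05, power 80%; sidedness is not stated. Sample size: "we are planning this study with 50 participants". Section 4c gives 120 instead.

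**Reproducing the plan's figure.**
- Difference: 70.6 − 50.1 = 20.5 mm.
- Pooled variance: (27.9² + 22.6²)/2 = (778.41 + 510.76)/2 = 644.6, so SD = 25.39 mm.
- Per arm, two-sided: 2 × (1.960 + 0.842)² × 644.6 / 20.5² ≈ 24.1, rounded up to 25. The total is 50, which matches 7c. A one-sided test gives 38, so two-sided is assumed below.
- Exact power (noncentral t) is 79.9% at 25 per arm and 99.2% at 60 per arm.

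**Assumptions not in the documents.** There are two anesthesia types, balanced within arm. A share p of patients is under a type whose mean 2-hour VAS differs by d mm from the other, equally in both arms. The within-type SD is 25.39 mm. The comparison is made directly at 2 hours.

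**Standard error and actual test level.** Leaving type out adds p(1 − p)d² to the residual variance. The ratio of estimated to true standard error is R = √[(644.6 + p(1 − p)d²)/644.6]. The actual two-sided error is 2 × [1 − Φ(1.96R)].

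| p | d (mm) | p(1 − p)d² | R | Actual error |
|---|---|---|---|---|
| 20% | 10 | 16 | 1.012 | 0.047 |
| 50% | 10 | 25 | 1.019 | 0.046 |
| 20% | 20 | 64 | 1.048 | 0.040 |
| 30% | 30 | 189 | 1.137 | 0.026 |
| 50% | 30 | 225 | 1.161 | 0.023 |

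**Power.** Simulated stratified trials (40,000 per setting, even split), analyzed without and with the type term; 52 patients stand in for 50 so that both strata are even.

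| N | d (mm) | Power without term | Power with term | Error without term |
|---|---|---|---|---|
| 52 | 0 | 81% | 81% | 5.1% |
| 52 | 10 | 80% | 81% | 4.8% |
| 52 | 20 | 77% | 81% | 3.5% |
| 52 | 30 | 71% | 81% | 2.2% |
| 120 | 20 | 99% | 99% | 3.4% |
| 120 | 30 | 98% | 99% | 2.3% |
| 120 | 40 | 97% | 99% | 1.3% |

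Hand check at N = 52, d = 30. The true standard error is 25.39 × √(4/52) = 7.04 mm and the estimated one is 7.04 × 1.161 ≈ 8.18 mm. Power ≈ Φ[(20.5 − 2.009 × 8.18)/7.04] = Φ(0.58) ≈ 72%, in line with the simulated 71%. With the term included, the error rate is about 5% throughout.

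**Precision of by-type estimates.** A 30% stratum of 50 patients is about 15 people. The 95% half-width for its arm difference is about 2.16 × 25.39 × √(2/7.5) ≈ 28 mm. For 36 people (30% of 120) it is about 2.03 × 25.39 × √(2/18) ≈ 17 mm.

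**The case against.** Most of the case against limits the size of the point; it does not remove it.

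- **The consequence is conditional.** A reader might infer that the error bars are simply wrong. The documents do not support that. They give no types, shares or residual effect at 2 hours, and at gaps of 10 mm or less the effect is negligible.
- **The direction is conservative.** Omitting a balanced stratum neither biases the arm difference nor adds false positives.
- **The plan is silent rather than explicit.** 7c does not say that types will be pooled, and a repeated-measures model can carry a between-patient factor. The fair description is an unspecified model.
- **The SD may already include differences between types.** It comes from a cited study of lidocaine before abdominal hysterectomy. If 25.4 mm is the total SD, power without the term stays at 81% or more. The error rate is still too low (3.3% at d = 20 mm and 1.5% at d = 30 mm; even split, 52 patients), and the term would add precision.

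A reader might also infer that a lingering anesthetic hides the block's effect in one type: with no effect in 30% of patients, the difference would shrink to 20.5 × 0.7 = 14.35 mm, unseen. This does not follow. With d = 30 mm the placebo mean in that type would be 70.6 − 30 = 40.6 mm, which section 7a classes as moderate pain (30–54 mm), so there would still be pain to reduce. Were the effect truly zero there, 14.35 mm would be the real average effect, which is what Aim 1 asks for. Nor would it be invisible: type is known for every patient, and a by-type look is merely unplanned. A main-effect term would not reveal such a pattern in any case.

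**Conclusion.** The point holds as a specification gap with a free remedy. The randomization uses anesthesia type and the primary analysis does not name it. If type is prognostic for 2-hour VAS, the standard error is overstated by 1–2% at a 10 mm gap, 5% at 20 mm with a 20% share, and 14–16% at 30 mm with a 30–50% share. The actual test level is then about 0.046–0.047, 0.040 and 0.026–0.023 respectively.

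With about 50 patients and an even split, power drops from about 81% to 77% (20 mm) or 71% (30 mm). With 120 it stays at 97% or above even at 40 mm. Which case applies depends on the totals in 4c and 7c, which conflict and need reconciling separately.

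These figures rest on two balanced types, a common shift in both arms and a within-type SD of 25.4 mm; none of these is given in the documents. The point does not show bias, false positives or a hidden treatment effect.

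**What to change.** In section 7c, state that the 2-hour VAS will be compared between arms in a linear model with arm and anesthesia type, the latter defined as the randomization stratum. If the Wilcoxon test is kept for non-normal data, use its version stratified by anesthesia type. List the anesthesia types that form the strata.

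Report the arm difference with its confidence interval for each type beside the overall estimate, labelled as descriptive. These estimates will be imprecise: half-widths are about 28 mm in a 30% stratum of 50 patients and about 17 mm in one of 120. They should not support subgroup claims.

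The cost is a few sentences. Anesthesia type must already be known for each patient in order to randomize, no new data are needed, and the 50 patients justified in 7c do not change on this account.

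### Section 4c sets 30 patients per arm at each of two sites, but section 7c names no site term; adding one is a nearly free improvement of modest size

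*Combined protocol and SAP*

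**What the plan says.** Section 4a names two hospitals. Section 4c gives the allocation by site: "We will randomize 120 patients total (60 at each site, 30 for placebo and 30 for treatment". The same paragraph specifies 1:1 permuted blocks and names one stratification factor, type of anesthesia. It does not say that the blocks are run separately at each site.

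The primary endpoint (section 2, Aim 1) is the mean difference in VAS at 2 hours. For VAS, section 7c says: "Visual analog pain scores will be compared using repeated measures of variance". Other continuous measures get a t test or a Wilcoxon test. Neither site nor anesthesia type appears in any of these analyses. Section 7c is silent on site; it does not state that the sites will be pooled.

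On care around the operation, section 4a says "The patients will receive their standardized anesthetic regiment per anesthesiology guidelines", and patients are then "monitored in the postoperative anesthesia unit for recovery per nursing guidelines".

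The sample size in section 7c is different: "we are planning this study with 50 participants". This conflicts with the 120 of section 4c. The conflict is a separate matter, but it affects how much a missing site term costs, so both sizes are shown below.

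**The concern.** When arms are balanced within each site, any site difference in mean pain falls equally on both arms and drops out of the arm difference. A test without a site term still counts that difference as patient-to-patient noise. The reported standard error then exceeds the true one, and the confidence interval does not match the allocation stated in section 4c.

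A site difference at 2 hours is plausible. Section 4a refers anesthesia and recovery to guidelines, and the protocol does not fix their content. Whether the two hospitals actually differ cannot be learned from the documents. At stake are the width of the interval for the primary comparison and, in a small trial, some power.

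**Working it through.** **Inputs from section 7c.** Two-hour VAS was "1% lidocaine (50.1 ± 27.9) compared to placebo (70.6 ± 22.6", so the difference is 70.6 − 50.1 = 20.5 mm. The common SD is √((27.9² + 22.6²)/2) = 25.39 mm. The error rate is given as "The Type I error probability associated with the test of this null hypothesis is 0.05", with 80% power; sidedness is not stated.

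**Reproducing the plan's figure.** A two-sided test at 0.05 with 80% power gives 25 per arm, 50 in total, as the plan has it (t-test power at 25 per arm is 79.9%). A one-sided test gives 38. Two-sided is therefore used throughout.

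**Assumption.** The gap D between sites in mean 2-hour VAS is not in the documents. A range of 0 to 30 mm is used.

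**Case 1: the split is enforced, 120 patients, 30 per arm at each site.** Two equal sites D apart add D²/4 to the apparent variance.

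- True SE = 25.39 × √(2/60) = 4.64 mm, at every D.
- Reported SE without a site term = 4.64 × √(1 + D²/(4 × 25.39²)).

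The SEs and half-widths follow from these formulas. Type I error, coverage and power come from 40,000 simulated trials per setting.

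| D (mm) | Reported SE | Excess | 95% half-width (mm) | Type I error | Coverage | Power, no site term / site term |
|---|---|---|---|---|---|---|
| 0 | 4.64 | 0 | 9.2 | 5.0% | 95.0% | 99.2% / 99.2% |
| 5 | 4.66 | 0.5% | 9.2 | 5.1% | 94.9% | 99.2% / 99.2% |
| 10 | 4.72 | 1.9% | 9.4 | 4.6% | 95.4% | 99.1% / 99.2% |
| 20 | 4.98 | 7.5% | 9.9 | 3.6% | 96.4% | 98.8% / 99.2% |
| 30 | 5.38 | 16% | 10.7 | 2.3% | 97.7% | 98.2% / 99.3% |

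SE, half-width, type I error and coverage are for the analysis without a site term. With the term, coverage stays near 95% at every D, and the estimate is unbiased in both analyses.

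**Case 2: the split is only a target, 120 patients.** Treatment was allocated at random across 60 + 60 patients, 20,000 simulated trials. At D = 20 mm the unadjusted test has type I error 4.9%, an empirical SE of 4.96 and a mean reported SE of 4.98. The unadjusted SE is valid. A single trial can still end unbalanced: with 35/25 at one site and 25/35 at the other, a 20 mm gap moves the unadjusted difference by 20 × (35/60 − 25/60) = 3.3 mm. That is chance variation which the SE already covers; a site term removes it.

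**Case 3: 50 patients, the plan's 20.5 mm difference.** The documents give no per-site split for this size, so 25 per site is assumed. Twenty-five cannot be halved, so the simulation used 13/12 at one site and 12/13 at the other. Power without and with a site term was 80.4% and 79.8% at D = 10, 78.8% and 80.0% at D = 20, and 75.1% and 80.1% at D = 30. The losses are about 1 point at 20 mm and 5 at 30 mm.

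These losses are flattering to the unadjusted test. The leftover imbalance shifts its estimate by D × (13/25 − 12/25) = 0.04 × D, and in that layout the shift enlarged the apparent effect. The shift can be taken out by arithmetic. With true SE 25.39 × √(2/25) = 7.18 and critical value 2.011, power ≈ Φ((20.5 − 2.011 × reported SE)/7.18):

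- Site term: (20.5 − 2.011 × 7.18)/7.18 = 0.84, about 80%.
- No site term, D = 20: reported SE 7.18 × 1.0748 = 7.72; (20.5 − 15.52)/7.18 = 0.69, about 75.6%.
- No site term, D = 30: reported SE 7.18 × 1.1615 = 8.34; (20.5 − 16.77)/7.18 = 0.52, about 69.8%.

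With exact balance the losses are therefore about 4.5 and 10 points. If the odd patients fall the other way, they are larger still.

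**The case against.** The strongest objection is that site is not a named stratifier. Sections 4a and 4c name only anesthesia type, so the 30/30 figure may be an enrollment target. Under that reading the unadjusted SE is valid (case 2). This stands, and it limits the point: the SE is too large only if the split is enforced.

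The gap D is also unsupported by any figure in the documents. Gaps of 20 to 30 mm are about as large as, or larger than, the treatment effect being sought. At 10 mm or less the excess is about 2% or below, and it is zero if the sites do not differ. This stands too.

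A third objection is that a repeated-measures analysis may absorb site. A constant site shift does cancel from within-patient change, but a shift specific to 2 hours, from anesthesia or recovery practice, does not. Section 7c does not say what the model contains.

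A reader might infer more than this:

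- That the error bars are simply wrong, or that false positives rise. Under an enforced split the only error is in the conservative direction; under a target there is no error.
- That both an oversized SE and a shifted estimate afflict the trial. They need opposite premises about the split, apart from losses after randomization.
- That power suffers at 120 patients. At the plan's own difference it does not, to any practical extent.
- That different surgeons operate at the two sites, or that each hospital follows its own guidelines. The documents say neither. Section 4a calls the anesthetic regimen standardized, and section 8b asks only for a trained urogynecologist.

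**Conclusion.** The point holds as a modest improvement. Section 4c states an allocation by site, and section 7c names no analysis that reflects it. If the split is enforced and the sites differ, the SE of the 2-hour difference is overstated by about 0.5% to 16% over assumed gaps of 5 to 30 mm. With 120 patients the 95% half-width grows from 9.2 mm to at most 10.7 mm, and power at 20.5 mm stays at 98% or more.

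Only at 50 patients and gaps of 20 mm or more does the omission matter for power. The loss there is 1 and 5 points (at 20 and 30 mm) in the layout that favors the unadjusted test, and about 4.5 and 10 points with exact balance.

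These figures rest on the SDs in section 7c, a common SD in both arms, equal-sized sites, a direct comparison at 2 hours, and a site gap that the documents do not give. The same reasoning applies on firmer ground to anesthesia type, which is a named stratifier and is also absent from the analysis.

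**What to change.** In section 7c, estimate the 2-hour VAS difference and its 95% confidence interval from a linear model with arm, site and anesthesia type. Use the same terms for the O'Leary-Sant and PUF comparisons. In section 4c, state whether the randomization lists are separate by site. The model is sensible under either answer, so it need not wait for this. Fix the wording before unblinding.

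The cost is one sentence in section 7c, one degree of freedom for site (and one fewer than the number of anesthesia types for that factor), and no new data.

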At the completion of the study if patients receive a significant improvement in their symptoms after hydrodistention and pudendal nerve block then they will continue to be managed with this therapy in the future. If they do not receive benefit or their participation ends prematurely they will be offered alternative therapies to treat their IC/PBS symptoms.

5. Inclusion/Exclusion Criteria

Inclusion Criteria: All women aged greater than 18 years of age scheduled to undergo cystoscopy with hydrodistention who are literate, English speaking and can provide written informed consent will be included in this study.

Exclusion Criteria: Patients who have intolerance or known allergies to local analgesia will be excluded. In addition, patients who have coagulation disorders will also be excluded as this may increase their risks of complication from bleeding. Patient will also be excluded if they have a history of dementia as this may impair their ability to follow instructions. Patients who are non-ambulatory and who have an inability to fully assess pain will

also be excluded. Patients receiving additional surgical procedures will be excluded from the study, as the source of their pain may be difficult to decipher in the immediate post-operative period.

6. Drugs/ Substances/ Devices

- a. The rationale for choosing the drug and dose or for choosing the device to be used.

Total 20cc (10cc bilateral) of 1% Lidocaine: Lidocaine is a commonly used anesthetic agent suitable for infiltration, block and surface anesthesia, It is characterized by a rapid onset of action, intermediate duration of efficacy, and its elimination half-life is 90-120 minutes. Lidocaine alters signal conduction in neurons by blocking the fast voltage gated sodium (Na) channels in the neuronal cell membrane that are responsible for signal propagation³¹. With sufficient blockage the membrane of the postsynaptic neuron will not depolarize and will thus fail to transmit an action potential. This creates the anesthetic effect by not merely preventing pain signals from propagating to the brain but by stopping them before they begin. Adverse drug reactions are rare when lidocaine is used as a local anesthetic and when administered correctly²⁷.

- b. Justification and safety information if FDA approved drugs will be administered for non-FDA approved indications or if doses or routes of administration or participant populations are changed. n/a

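### Could participants removed after randomisation under section 4f drop out of the 2-hour VAS comparison?

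*Combined protocol and SAP*

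**What the plan says.** - **Removal (section 4f).** "Participants may be removed from the study if they are diagnosed/newly recognized to meet any of the exclusion criteria, including intolerance of local anesthesia". Another listed reason is "new onset mental status change that precludes the patient from being able to follow instructions or accurately assess pain control". Removal is optional, has no time limit, and comes with no instruction about data already collected.
- **Related exclusion (section 5).** "Patients who have intolerance or known allergies to local analgesia will be excluded". Having additional surgical procedures is also an exclusion.
- **Intention to treat (section 7c).** "an intention to treat analysis will be performed for the participants who drop out prior to study completion". No primary analysis set is defined by name, and there is no rule for a missing score.
- **VAS analysis (section 7c).** "Visual analog pain scores will be compared using repeated measures of variance".
- **Treatment (section 4a).** Participants are randomised to "20 cubic centimeters 1% lidocaine or 20 cubic centimeters normal saline after anesthesia induction". The circulating nurse holds the sealed allocation, and the surgeon receives a syringe labelled only with the name of the procedure.
- **Timing (section 8b).** Participants are "monitored in the postoperative recovery area for 2 hours after their procedure", which is also when the primary VAS is taken.
- **Early exit (section 4g).** This covers later care only, not data.

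**The concern.** Randomisation follows induction of anaesthesia, so some reasons for removal can first appear after allocation: a reaction to the injected drug, a change in mental status, or an unplanned additional procedure. Intolerance revealed by the study injection can arise only in the lidocaine arm, because the comparator is saline. A non-study anaesthetic could reveal it in either arm.

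Section 7c attaches intention to treat to those who drop out, and a participant removed by the investigator need not be called a dropout. Read narrowly, the plan leaves her place in the primary comparison open. If it were settled once arm and pain score were known, the groups formed by randomisation could be altered selectively. A repeated-measures analysis run on complete cases could also lose a 2-hour score when later ratings are missing.

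**Working it through.** **1. The plan's own figure.** Section 7c gives means (SD) of 50.1 (27.9) and 70.6 (22.6), alpha 0.05, power 80% and 50 participants.

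- Difference: 70.6 − 50.1 = 20.5 mm.
- Pooled SD: √((27.9² + 22.6²)/2) = 25.39 mm.
- n per arm, two-sided: 2 × (1.960 + 0.842)² × 25.39² / 20.5² = 24.1, rounded up to 25, so 50 in total. This matches.
- Power at 25 per arm: 81.5% by normal approximation, 79.9% by the noncentral t.

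Section 4c instead randomises 120 (60 per arm), so both sizes are carried below. That mismatch is a separate matter.

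**2. Who could be affected.**

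| When removed | 2-hour VAS | What the wording decides |
|---|---|---|
| Before randomisation | None needed | Nothing; not in a randomised comparison |
| After randomisation, before 2 hours | Probably missing | Little; naming the analysis set does not supply a score |
| After 2 hours | Already collected | Whether the score is kept; nothing says it is discarded |

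Only the last row turns on the wording, and there the ordinary meaning of intention to treat keeps the score.

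**3. Size under an adverse assumption.** No removal rate is given. The nearest figure is in section 8a: "these risk include a less than 1% chance of additional pain, bleeding, hematoma or lidocaine systemic toxicity". That describes risks of the block, not removals, and does not measure additional surgery or other newly found ineligibility. So 1% removed, in the lidocaine arm only, is an assumption and not an upper limit. Expected removals are 25 × 0.01 = 0.25 or 60 × 0.01 = 0.6 participants.

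Simulated two-sided pooled t-test under the null (both arms SD 25.4, scores capped at 0 to 100, common mean 50.1 to 70.6):

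| Who is removed (1%) | Shift in lidocaine mean | Type I error |
|---|---|---|
| No removal | 0 mm | 5.0% |
| Unrelated to pain | 0 mm | 5.0% |
| Always the highest score | −0.3 to −0.5 mm | 5.3–5.7% |
| Always the lowest score | +0.5 to +0.6 mm | 5.4–5.8% |

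At 2%, with equally extreme selection and common mean 50.1, the shift is about 1 mm. Error is then about 6% at 25 per arm and 6.5% at 60 per arm.

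The t-test is not the analysis that section 7c names for VAS. A five-time-point group-by-time F test (equal correlation of 0.3, 0.5 or 0.7 assumed, removed participants dropped at every time) gives 4.9–5.3% at 1% extreme removal, against 4.9–5.1% with none. That is no clear change.

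**4. Power at the stated 20.5 mm and SDs, 25 per arm, uncapped scores.** About 79.9% with no removal, and about 78% to 82% at the 1% extremes. (Capping scores at 0 to 100 shrinks the simulated difference to about 19.5 mm, so capped power runs are not used here.)

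**5. A wider range.** If a fraction r of one arm is removed and those participants average k mm above the rest, the arm mean moves by r × k. For assumed r of 2% to 10% and k of 10 to 30 mm, this runs from 0.02 × 10 = 0.2 mm to 0.10 × 30 = 3.0 mm. The top of that range needs both extremes at once and is 3.0/20.5 = 15% of the planned difference.

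**The case for a change.** The strongest case for a change is that the membership of the primary comparison should be fixed before outcomes are seen, and that a few sentences would do it without touching clinical care. The text does leave room: section 4f is discretionary, section 7c speaks only of dropouts, and no other section defines the analysis set. Section 4c says assignment is revealed in the operating room without saying to whom, and nothing in section 4f requires a removal decision to be blind. Nor is the 1% figure a bound on all removal reasons.

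The ambiguity stands, and so does the point about the 1%. The step from there to a likely harm does not. The protocol declares the trial double-blind, and the unmarked syringe in section 4a supports that, so a removal decided with knowledge of arm would depart from the design. The complete-case worry is hypothetical, since section 7c does not specify complete cases, and it concerns ordinary loss to follow-up more than removal. For anyone removed before 2 hours, a sentence placing all randomised participants in the analysis would still need a missing-data rule before it could be carried out.

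**Conclusion.** No change follows. This is missing detail that analysts can be expected to fill in the usual way: analyse randomised participants in their assigned arm and keep scores already collected. The plan commits to intention to treat for those who leave before completion, and nothing in it points to excluding removed participants. Spelling this out would be tidier but would not alter the analysis a competent statistician would run.

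At an assumed 1% removal confined to the lidocaine arm and always taking the extreme score, the shift is roughly half a millimetre and the error at most about 5.8%. The direction is unknown, and removal unrelated to pain gives no bias. The conclusion rests on removals being rare, on blinding being maintained as declared, and on intention to treat carrying its ordinary meaning. A removal rate near 10% with strong selection on pain would weaken it, but nothing in the protocol suggests that.
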